#### I. HYPOTHESES AND SPECIFIC AIMS:

This Human Subjects Research involves a pilot trial using a pre/post design to simultaneously to evaluate the feasibility, acceptability, and preliminary effectiveness of a weight management intervention, Community Active and Healthy Families (Community-AHF), at reducing child body mass index (BMI).

Study Aim: To pilot Community-AHF among 5–12-year-old overweight and obese Latino children in immigrant families (n=40 parent/child dyads) using a pre/post design

- We will examine changes in child BMI (primary outcome) and in diet, physical activity, and parenting skills/stress (secondary outcomes) pre- and post-intervention to assess for indicators of intervention effectiveness and to gather the information needed to refine measures, and measurement procedures in preparation for a pragmatic randomized controlled trial.
- We will evaluate pilot implementation via assessing program acceptability and feasibility. We hypothesize that families
  will report high levels of program acceptability and that implementing community organizations/clinics will report high
  levels of program feasibility and an intention to maintain participation in a future trial. We will also conduct qualitative
  interviews to explore implementation successes and challenges to guide refinement of implementation protocols for a
  future trial.

#### II. BACKGROUND AND SIGNIFICANCE:

Effective, family-oriented childhood weight management interventions for Latinos are critical in order to decrease lifetime cardiovascular disease (CVD) risk that stems from childhood obesity. Childhood obesity is a risk factor for adult CVD, the leading cause of death in the US. One in four US children is Latino and Latino children have among the highest childhood obesity rates of any racial/ethnic group. US-born Latino children of immigrant parents comprise half of US Latino children and experience higher obesity rates than other Latino children. Obesity rates among Latino children have increased during the COVID-19 pandemic. In parallel with obesity prevention efforts, a specific focus on treatment is urgently needed.

Implementation of current US Preventive Services Task Force (USPSTF) recommendations for childhood obesity has the potential to exacerbate existing disparities for Latino children in immigrant families. The USPSTF recommends referral of all children with obesity to an intensive weight management program to prompt behavior changes to decrease body mass index (BMI). Intensive programs are found mainly in clinical settings, are limited in number and frequently are not feasible for Latino immigrant families. Sustaining participation of Latino immigrant families in intensive community-based programs has been difficult due to the time commitment required and cultural and language barriers. Reducing obesity disparities for Latino children in immigrant families requires addressing the current lack of evidence-based obesity treatment programs that are tailored to their sociocultural needs and delivered at a feasible intensity.

We propose addressing this gap with the Community-Active and Healthy Families (Community-AHF) intervention. Community-AHF is a behavioral-theory based, culturally tailored, Spanish-language weight management program for overweight/obese Latino children and their families. Community-AHF has recommended USPSTF components of intensive weight management delivered at a feasible intensity for low-income families. To create Community-AHF, we engaged partners to complete Intervention Mapping to adapt an evidence-based weight management intervention designed for low-income Latino children in immigrant families delivered in healthcare settings. Community-AHF retains key components of the original intervention and responds to feedback from Latino immigrant families that delivery in a community setting is preferable to a clinic due to easier access to and greater trust and familiarity with community organizations.

Intervention delivery in a community setting requires critical attention to how this change in delivery setting may impact intervention components and their implementation. We engaged key partners using community-based participatory research (CBPR) principles to identify adaptations of Clinic-AHF to allow for community delivery via a systematic process, Intervention Mapping-Adapt. This process has been used successfully in adapting and implementing health interventions among immigrant Latinos in the US. The use of this process ensures that Community-AHF retains Clinic-AHF essential components while incorporating adaptations required of the new delivery setting. While Intervention Mapping-Adapt was the appropriate element of Intervention Mapping for adaptation, Implementation Mapping, is the right process to ensure "how" the core components of the intervention are delivered meets partners' needs and priorities.

#### II. RESEARCH METHODS

## A. OUTCOME MEASURE(S):

Change in child body mass index, diet, physical activity, obesogenic food availability in the home, parent physical activity

promotion, parenting self-efficacy, parent perceived stress, intervention acceptability, feasibility, intervention fidelity

#### B. DESCRIPTION OF POPULATION TO BE ENROLLED:

Community-AHF Pilot enrollment is for six (6) months. For this part of the study, we will be relying on primary care referrals or community based referrals.

- Inclusion Criteria: 1) Child aged 5-12; 2) Child BMI > 85th %tile; and 3) Parent self-identifies as foreign-born Latino/Hispanic and speaks Spanish.
- Exclusion Criteria: Child medical contraindication to diet/PA modification and Child BMI ≥40kg/m² (obesity this severe needs subspecialty management)

# C. STUDY DESIGN AND RESEARCH METHODS:

# Study Design:

We will recruit child-parent dyads from one primary care pediatric practice in both CO and MD or via outreach by our community partner in CO. We will recruit 20 child-parent dyads at each site. We will enroll 40 overweight (BMI≥85th%ile for age and sex) or obese (BMI≥95th%ile for age and sex) 5–12-year-old patients and a parent/guardian. We will examine changes in the anticipated trial outcomes. We will assess intervention acceptability and feasibility to parents and examine preliminary effectiveness. The primary effectiveness outcome will be a change in BMI from baseline to follow up. Secondary outcomes reflect key features of the intervention curriculum that promote child and family behavior change including child diet and PA, home food environment, parent PA promotion and parenting self-efficacy. We will also conduct a preliminary implementation evaluation. If two (2) children in the same household are eligible, one will be randomly selected to be in the index child participant.

Community AHF is a 10-month intervention with 20 contact hours (16 in person during the active phase and 4 virtual during the maintenance phase). Each index child participant must be accompanied by a parent; additional parents/caregivers and siblings of the index child may attend. This pilot will evaluate the active phase of the intervention *only* given the time constraints of this funding mechanism. Effectiveness data for the evidence-based intervention from which Community-AHF was adapted is based on the 4-month active phase.  During the 4-month active phase participants attend eight 2-hour semimonthly group education sessions. Sessions follow a curriculum and provide: 1) Practical information to increase knowledge and perceived importance of healthy diet and PA practices; 2) Skill building in problem-solving and positive parenting to overcome barriers to behavior change at the child and family-level; 3) PA; and 4) Facilitated supportive discussion to assist parents in managing stressors and SDOH barriers to healthy weight.

Each session covers specific objectives and includes complementary hands-on activities and breakout groups for children (children's breakouts are often conducted in English). At the conclusion of each session participants receive take-home materials to facilitate behavior change. Sessions are co-facilitated by a registered nurse and CHW. Additionally, participants complete 7 CHW coaching calls (15-20 minutes) during weeks without a group session to reinforce change goals and discuss successes and challenges meeting these goals. During the 6-month maintenance phase which will be employed in a future trial, participants will complete monthly, 20-minute coaching calls, attend a primary care obesity follow-up visit, and attend a concluding celebration. Community-AHF will be delivered by trusted community organizations well-known to the local Latino community and experienced in providing community programming.

We will also complete a qualitative evaluation of the Community-AHF pilot and its implementation. We will interview a subset of parents and youth who participate in the intervention for this portion. These interviews will take place after the completion of the pilot.

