Parent-completed surveys during home visits will include information on parent, child and family sociodemographic characteristics, covariates of interest (e.g., child sleep and screen media use) and scales/measures used to determine secondary outcomes. Family sociodemographic characteristics will be measured at baseline only. The follow-up survey will include brief measures of satisfaction with the Community-AHF intervention, acceptability and feasibility. Parent-completed surveys will be administered via guided oral administration by the research staff member and all answers will be entered directly into a REDCap electronic survey form to allow for simultaneous data capture and storage. The exception to this is the responses to the secondary outcome diet measure (Block Hispanic Food Frequency Questionnaire) which will be entered into a proprietary web interface provided by NutritionQuest. We have used guided oral administration in our past research with similar study populations to allow for survey completion by populations with limited literacy and who may be unfamiliar or uncomfortable with electronic survey formats. Participants will be given the option to complete the survey on their own via a study computer with the research staff member present.

Another data component of the home visits is a home food inventory that will be completed by the research staff members by visualizing food stored in the home and recording types of food and quantity. The parent completing the survey will guide the research staff member to food stored in the home. The research staff will record responses and home food inventory information into the REDCap electronic survey. The research staff member will also complete anthropometric measurements to calculate BMI by twice measuring height to the nearest 0.1cm and weight (light clothing, no shoes) to the nearest 0.1kg using stadiometers (Hopkins Road Rod) and portable digital scales (Seca 874), respectively. All anthropometric measurements will be recorded in REDCap by the research staff member. In lieu of a home visit, participants can complete data collection visits in a private space at either of the research institutions involved in the proposed work or at the community organization.

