### F. DATA ANALYSIS PLAN:

### Indicators of Effectiveness

As this is a pilot study, we will not be powered to detect statistically significant differences pre- and post- intervention. We will measure the average change in %BMIp95 between baseline and completion of the Community-AHF active phase. Without a counterfactual (control group) we will not be able assign responsibility to Community-AHF for any observed

improvements. Change in %BMIp95 across the study period will provide data to test our hypotheses and will inform statistical power analyses for a subsequent trial. This pre- and post-intervention data is ideal for generating sample size estimates for a larger randomized control trial in the same population.

We will conduct within-individual analyses for each outcome of interest. We will only analyze participants who contribute pre and post measures in order to avoid biases that can occur when analyses are conducted with all available data. For each outcome for which a participant contributes pre and post measurements, we will calculate pre and post means, standard deviations, differences in means and the p-value of the difference. We will conduct preliminary analyses of outcomes according to subgroups defined by rate of attendance at intervention sessions. If adequate data are available, we will explore the possibility of a nonresponse analysis.

All statistical analyses will be conducted using Mplus, or the latest version of R (specifically the nlme package).

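### Does it matter that the primary outcome is named as change in BMI but analysed as change in %BMIp95?

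*Combined protocol and SAP*

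**What the plan says.** The Hypotheses and Specific Aims section gives the purpose of the programme as being effective "at reducing child body mass index (BMI") and continues: "We will examine changes in child BMI (primary outcome"). The Outcome Measure(s) section opens its list with "Change in child body mass index, diet, physical activity, obesogenic food availability in the home". The Study Design section says "The primary effectiveness outcome will be a change in BMI from baseline to follow up". None of these gives a scale. The Research Methods section has staff "complete anthropometric measurements to calculate BMI by twice measuring height to the nearest 0.1cm", with weight also measured twice, and goes no further than BMI.

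The Data Analysis Plan, under Indicators of Effectiveness, says: "We will measure the average change in %BMI p95 between baseline and completion of the Community-AHF active phase". It adds that this change will serve to test the study's hypotheses and to inform power for the next trial. The next paragraph says "We will conduct within-individual analyses for each outcome of interest" and, for participants with both measurements, "we will calculate pre and post means, standard deviations, differences in means and the p-value of the difference".

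%BMIp95 appears only in that section. It is not defined there and no growth reference is named.

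**The concern.** Raw BMI and BMI relative to an age- and sex-specific 95th percentile (P95) are different variables whenever P95 moves with age. The children are 5 to 12 years old, follow-up is at 4 months, and no control group absorbs normal growth. A raw BMI change includes that growth; %BMIp95 removes the part that is in the reference.

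Read literally, the first paragraph of the analysis plan yields a mean change in %BMIp95. The second yields a p-value for each listed outcome, and the outcome list contains body mass index, not %BMIp95. No sentence says which is the primary result. The same data could then be reported as no change in BMI or as a fall in %BMIp95, with the choice made after the results were seen. The mean and SD carried into the next trial's sample size would also depend on that choice.

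**Working it through.** **There is no figure of the plan's own to reproduce.** It gives no SD, effect size, significance level or power calculation. The only arithmetic available is 20 dyads at each of 2 sites = 40, which agrees with the stated enrolment.

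**How far apart can the two scales be?** Inputs from the documents: n = 40 and a 4-month interval. Everything else is assumed: P95 rises 0.4 to 1.0 kg/m² per year, the mean ratio BMI/P95 is 1.0 to 1.2, and the SD of the BMI change is 0.6 to 1.0 kg/m². %BMIp95 is taken as 100 × BMI / P95 at the child's age at each visit.

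Rise in P95 over the interval: g = annual rise × 4/12. On the BMI scale the reference moves by ratio × g, so the paired t statistics on the two scales differ by about ratio × g × √n / SD, with √40 = 6.325. If mean BMI is flat, t on raw BMI is 0 (p = 1.0), and the %BMIp95 result is:

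| Case | Annual rise | g | Ratio | SD | t on %BMIp95 | Two-sided p (39 df) |
|---|---|---|---|---|---|---|
| Low | 0.4 | 0.133 | 1.0 | 1.0 | −0.133 × 6.325 / 1.0 = −0.84 | 0.40 |
| Central | 0.7 | 0.233 | 1.1 | 0.8 | −0.257 × 6.325 / 0.8 = −2.03 | 0.049 |
| High | 1.0 | 0.333 | 1.2 | 0.6 | −0.400 × 6.325 / 0.6 = −4.22 | 0.0001 |

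- Size in points, central case with BMI 24.20 and P95 going from 22.00 to 22.233: 100 × (24.20/22.233 − 1.10) = −1.15.
- Mean BMI change of +0.10, central case otherwise: t = 0.10 × 6.325 / 0.8 = 0.79 (p = 0.43) on BMI, and (0.10 − 0.257) × 6.325 / 0.8 = −1.24 (p = 0.22) on %BMIp95. The signs differ, but neither result would be read as a change.
- Central case with 30 complete pairs (assumed): t = −1.76, p = 0.089.
- If P95 does not rise, g = 0 and the shift vanishes.

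A separate simulation used other assumptions: SD 0.8 to 1.2, mean BMI change −0.4 to +0.2, and P95 rising 0.1 to 0.3 kg/m² over the interval. The two scales fell on opposite sides of 0.05 in about 7% to 74% of trials at n = 40. So the scale can matter; the documents cannot say how much it matters here.

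**Does the plan leave the choice open?** Setting the sections side by side:

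- The aims examine child BMI, labelled primary, for signs of effectiveness. The analysis section headed Indicators of Effectiveness names one body-size measure, %BMIp95, and no raw BMI analysis.
- The interval is the same. The Study Design section runs from baseline to follow-up and limits the pilot to the active phase; the analysis plan runs from baseline to the end of the active phase.
- %BMIp95 is given the uses a primary outcome would have: hypothesis testing and planning the next trial.
- The outcome list names constructs, not scales. Diet and physical activity also stand there without a scale, and their instruments (a food frequency questionnaire and an accelerometer) come later. BMI is treated in the same way.
- Elsewhere BMI is mostly expressed relative to age and sex, through percentiles in the eligibility and design text. Where a raw cut-off is meant, for the severe-obesity exclusion, the units kg/m² are given.

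These point one way: BMI is the construct and %BMIp95 is its analysed scale. A competing raw BMI p-value arises only if the phrase about each outcome is taken to exclude the one BMI measure named in the paragraph before it.

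**The case for a change.** The strongest reply is that all this is inference. No sentence says that the primary outcome is analysed as %BMIp95, the measurement section stops at BMI, and a literal analyst could produce a %BMIp95 mean and a raw BMI p-value. The only hypotheses that the aims state explicitly concern acceptability and feasibility, so the remark about testing hypotheses is a weaker link than it first appears. Even on the natural reading, the definition and the growth reference are absent. A pilot meant to refine measures for a later trial ought to be clear about its main one, and a few sentences would settle it at no cost in visits or measurements.

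The textual part of this stands: the definition, the reference and the explicit link are not written down. What does not follow is that the result is at risk. Raw BMI and %BMIp95 both come from the same height, weight, age and sex, so nothing is lost at data collection. The scale that the analysis plan names already takes account of reference growth, so writing the link down would confirm the expected analysis and not alter it.

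**Conclusion.** No change to the plan is needed. This is a small gap in specification that analysts following the Data Analysis Plan would fill sensibly, by reporting the primary BMI outcome as change in %BMIp95 against a stated growth reference.

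The possible gap between scales is real in principle: a shift in the paired t statistic of 0.84 to 4.22 with 40 pairs. That range rests almost wholly on assumed values for P95 growth, BMI/P95 ratio and SD, and it falls to zero if P95 does not move. The central p-value of 0.049 lies just under a threshold that the plan never sets, and it needs all 40 dyads to contribute both measurements.

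The consequence is also limited. The plan says that the pilot is not powered to detect pre/post differences and that, without a control group, improvement cannot be credited to the programme. No significance level is set and no decision depends on this p-value, so at most the matter affects how one descriptive result is labelled. The judgement rests on reading %BMIp95 as the scale of the BMI outcome, which the structure of the documents supports.

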### Retention -

Strategies include: 1) obtaining multiple methods of contact with updates at each point of contact with the study team and obtaining permission to extract contact information from the child's electronic health record; 2) establishing loss to follow-up protocols using multiple contacts for each method of participant contact; 3) creating a study identity through use of a logo and consistent fonts and colors on all study materials; 4) employing bilingual staff skilled at building relationships with immigrant study participants; 5) offering remuneration for participation in data collection; and 6) scheduling data collection visits based on participant preference including evenings and weekends.

### Consent -

Owing to the characteristics of our study population, we expect to utilize Spanish-language consent forms for parents and need to account for limited literacy of participants. We will utilize an informed consent process that we have previously found effective with the proposed study population. The research staff member will read the Spanish-language form aloud while the participant follows along with their own hardcopy, elicit, and respond to participant questions, and finally ascertain understanding via 2-3 brief questions (e.g., Will participants in the Community-AHF program complete surveys?) Participants will have as much time as necessary to review the consent form and ask questions.

We will complete an assent process for children ≥7 years of age participating in the Community-AHF pilot. A research staff member will discuss the research with the child in the presence of the child's parent or guardian. The assent process will discuss the purpose of the research study, what the participants would have to do in the research study, associated risks and benefits and emphasize that the participation is voluntary. We will have the child provide verbal assent, and this assent will be noted on the parent's consent form.

Signed consent forms will be kept in a locked file cabinet in a locked office. Participants will be provided with a copy of the consent form for their reference.

Additionally, we are requesting a waiver of consent and HIPAA authorization for the screening used to determine eligibility for children for the Community-AHF program.

#### Renumeration -

Participants in the Community-AHF pilot will receive the following remuneration: Survey-Baseline (\$75)
Survey-Follow Up (4 months after baseline) (\$75)
Accelerometer-Baseline (\$50)
Accelerometer-Follow Up (\$50)
Follow-up Interview-Parent (\$50) and Follow-up Interview-Youth (\$25)

### Research Methods:

Pilot dyads will complete the active phase of the Community-AHF intervention that includes eight (8), semimonthly 2-hour group education sessions for 16 weeks, and 8 biweekly coaching calls. Sessions follow a curriculum and provide: 1) Practical information to increase knowledge and perceived importance of healthy diet and physical activity practices; 2) Skill building in problem-solving and positive parenting to overcome barriers to behavior change at the child and family-level; 3) Physical activity; and 4) Facilitated supportive discussion to assist parents in managing stressors and social determinants of health barriers to healthy weight. Each session covers specific objectives, includes a number of complementary, handson activities, and provides participants with take-home materials to facilitate behavior change. Community-AHF will be delivered by a nurse and a Community Health Worker (CHW) trained by a consultant nutritionist and study investigators.

If the child has been referred by their pediatrician referring providers will also receive a communication regarding the family's participation. Once the child starts a cohort there will be an additional communication to the referring provider when the child completes the 4-month active phase. This communication will include a summary of family goals for healthy child weight, the current BMI, and a reminder that the child should have a follow up visit with the referring provider. The consent process will include specific permission for this release of information to the referring provider and/or signing of a separate release of information of form based on IRB determination.

Parent-completed surveys during home visits will include information on parent, child and family sociodemographic characteristics, covariates of interest (e.g., child sleep and screen media use) and scales/measures used to determine secondary outcomes. Family sociodemographic characteristics will be measured at baseline only. The follow-up survey will include brief measures of satisfaction with the Community-AHF intervention, acceptability and feasibility. Parent-completed surveys will be administered via guided oral administration by the research staff member and all answers will be entered directly into a REDCap electronic survey form to allow for simultaneous data capture and storage. The exception to this is the responses to the secondary outcome diet measure (Block Hispanic Food Frequency Questionnaire) which will be entered into a proprietary web interface provided by NutritionQuest. We have used guided oral administration in our past research with similar study populations to allow for survey completion by populations with limited literacy and who may be unfamiliar or uncomfortable with electronic survey formats. Participants will be given the option to complete the survey on their own via a study computer with the research staff member present.

Another data component of the home visits is a home food inventory that will be completed by the research staff members by visualizing food stored in the home and recording types of food and quantity. The parent completing the survey will guide the research staff member to food stored in the home. The research staff will record responses and home food inventory information into the REDCap electronic survey. The research staff member will also complete anthropometric measurements to calculate BMI by twice measuring height to the nearest 0.1cm and weight (light clothing, no shoes) to the nearest 0.1kg using stadiometers (Hopkins Road Rod) and portable digital scales (Seca 874), respectively. All anthropometric measurements will be recorded in REDCap by the research staff member. In lieu of a home visit, participants can complete data collection visits in a private space at either of the research institutions involved in the proposed work or at the community organization.

Regarding physical activity measurement using accelerometers, research staff will provide the index parent/child dyad with a ActiGraph GT9X Link accelerometer at each data collection home visit and instruct them to have their child to wear it like a watch on the non-dominant wrist for seven consecutive days and nights and to remove it only for aquatic activities (e.g., swimming, bathing) and group sports that prohibit wearing jewelry or watches (e.g., basketball, soccer). Study staff will provide participants with contact information for any questions/concerns about the accelerometer. After 7 days, participants will return the accelerometers to the community organization involved in the study or via prepaid protective envelopes based on participant preference. After receiving the device, research staff will wipe it with the alcohol disinfecting cloth, download the data and set it up for redistribution to the next participant.

